#### 5.4. Intervention and follow-up

The intervention and follow-up of participants will begin after the conditions eligible to participate in the study are verified, proceeding as follows:

5.4.1. For selected participants with pre-existing risk factors, these are: immediately previous pregnancy terminated prematurely with preterm birth, or premature rupture of membranes before 35 weeks of gestation; placement of a progesterone cerclage pessary, or treatment with progesterone capsules will start at week 16 (0/7) but not beyond 24 (0/7) weeks of gestation. These participants will have a transvaginal ultrasound performed to document the length ( $\geq 10$  mm) and position of the cervix at the placement of the pessary or the start of treatment with vaginal progesterone capsules.

5.4.2. For pregnant patients with a single fetus, selected for the presence of a shortened cervix (between 10 mm and 25 mm), the pessary will be inserted or the vaginal administration of progesterone capsules will be started at the time of the investigation, but not before 16 (0/7) weeks of gestation and not after 24 (0/7) weeks of gestation. The cervix angulation relative to the uterus body using the intersection of the uterus posterior wall longitudinal axis with the cervical canal axis in addition to a measurement of the cervical length will be performed on 60% of the study participants assigned to one of the two groups with medicated pessary, prior to insertion of the pessary and after its insertion, by means of a transvaginal ultrasound technique recently described (25). The transvaginal ultrasonography post-insertion of the pessaries may be performed at visit one or at visit two at the latest.

5.4.3. After insertion of the pessary or beginning of the administration with vaginal progesterone capsules and until 28 weeks of gestation, participants in the 3 treatment groups will be monitored every 4 weeks at the most or more often, if the site has established so as a control standard. After 28 weeks, patients should be monitored every 2 weeks. At every control visit, procedures applicable to their prenatal control and a transvaginal ultrasound by standard technique will be performed (patients receiving vaginal capsules), if considered necessary by the physician, or transvaginal using the technique recently described (25) (in patients with medicated pessary) to measure and record cervical length. The occurrence of possible side effects, adherence to treatment, and visits or hospitalizations due to threat or preterm labor will also be recorded, as well as the existence of potential causes for *ex-post* exclusion from the study. In addition, concomitant medication will be recorded at each visit.

5.4.4 Management of participants consulting due to a threat or premature labor will be conducted according to the diagnostic and therapeutic guidelines of the Ministry of Health (MINSAL) (Clinical Guide for Preventing Preterm Birth - MINSAL 2010) and the respective hospital's Obstetrics and Gynecology Service. In these cases, the treating physician will be provided with information about the progesterone treatment the patient is receiving in the study, and the decision for her continuation in the clinical study will be made jointly as far as possible, since the opinion of the treating physician shall predominate.

5.4.5 Every case will be closed at 36 6/7 weeks of gestation, or at the time of preterm birth. Data on the birth, condition at birth, and evolution of infants born preterm will be analyzed, recording morbidity and mortality through the time of discharge from the hospital.

The participant's attending health team (physicians and midwives) will be informed in writing about the participation of these women in the study by means of an identification

card that will be given to every woman participating in the study. In the pregnancy card, participation of these subjects in the study will be emphasized by means of a self-adhesive sticker detailing their participation in one of the treatment groups (pessary or capsule) and recorded in the medical history.

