#### 5.5. Placement and repositioning of the cerclage pessary containing sustained-release progesterone

Once the cervix length and positioning have been examined by transvaginal ultrasound, and any vaginal infection has been ruled out or treated, the progesterone pessary should be implanted by a professional qualified and trained for that purpose. For placement, the participant must be lying in supine position.

The removal of the pessary will be done by vaginal examination at week 36 6/7 or earlier, if there is any medical indication for induction of premature labor or elective cesarean section. The pessary will also be removed from participants in preterm birth labor not responding to treatment with tocolytics.

During controls or visits to emergency departments or medical offices, participants who report vaginal discharge should be examined by a physician to rule out infection by relevant testing (vaginal discharge smears for PCR), and deliver the appropriate treatment without the need to remove the pessary. This condition will be considered an adverse event.

In the event that the medicated cerclage pessary is spontaneously expelled it, will be repositioned within maximum 72 hours; if this does not occur, the patient will be withdrawn from the study but considered in the final statistical analysis under the intention-to-treat principle.

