5. ANALYSIS CONVENTIONS

The statistical analysis will be made by ILS Clinical Research under the authorization of Laboratorio Andromaco S.A.

GENERAL PRINCIPLES

The statistical analysis will be provided to give a general summary of the study subjects and a vision of the efficacy and safety of the results. The data provided by the sites will be summarized for this purpose. Tables of absolute and relative frequencies will be constructed for the quality variables. All the percentages will be presented with a decimal. The quantitative variables will be summarized with the number of subjects participating (n), mean, standard deviation (SD), and median, maximal and minimal.

Two tailed test will be carried out for all the analysis and the type I error is 0.05 for continuous variables and the discrete variables. All p values shall be rounded to three decimal and the values under 0.001 will be presented as <0.001 and values greater than 0.999 will be presented as 1.000. A comparison of the treatment groups will be done with respect to the demographic and baseline characteristics using inferential statistical techniques to detect if any of these variables may condition the results in the dependent variables. Comparisons in qualitative variables will be carried out using the Cochran-Mantel-Haenszel (CMH) test of general association, while the comparisons in quantitative variables will be made with a test of comparison of means (ANOVA analysis of variance) for independent samples with normal distribution. In the cases of no normality on the continuous variables, or in case of not belonging to the exponential family for discrete data, the parametric tests will be replaced for nonparametric tests such as Kruskal-Wallis or Friedman. These tests will be presented in each table as deemed necessary. All confidence intervals will be two-tailed and at 95%.

Table 1: Study Schedule of Assessments

Activities	Visit 1	Visit 2	Visit 3	Visit 4	Visit 5	Visit 6	Visit 7	Final Visit
Demography	X							
Medical History	X							
Physical Exam	X	X	X	X	X	X	X	X
Gynecological Exam	X							
Vital Signs	X	X ¹	X ¹	X ¹	X ¹	X ¹	X ¹	X ¹
Transvaginal Ultrasound	X	X ²	X	X	X	X	X	X
Pre-birth Control	X							
Obstetric Background	X							
Lab Tests (Blood and Urine)	X							
Eligibility	X							
Vaginal Discharge	X	X ³	X ³	X ³	X ³	X ³	X ³	X ³
Randomization	X							
Pessary Insertion	X							
Acceptability and tolerance to the insertion	X							X
Concomitant Medications	X	X	X	X	X	X	X	X

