Occurrence of membranes' ruptures: Premature rupture of membranes after 32 weeks but before 34 weeks of gestation. The Cochran-Mantel-Haenszel (CMH) test will be used, where the incidence of rupture of membranes in each group will be compared and will be identified through the registration of adverse events.

Anatomical cervical changes (Only groups B and C): The length of the cervix and cervical angle variables, will be described as continuous and measured variables through time, using the test of comparison of means through the Analysis of Variance (ANOVA) for repeated measures, considering the baseline result as a covariate in the comparison and shall be based on the sum of squares type III. The difference between groups regarding the change from baseline will be assessed through t tests paired within ANOVA, utilizing the difference in means estimated by least squares. These comparisons will be made amongst all treatment groups with pessary.

Acceptability and tolerability of insertion (only groups B and C):

Acceptability and tolerability will be assessed through a questionnaire which must be completed at the beginning and end of the study. Questions (i) and (ii) are answered at visit 1, question iii (VAS) is answered at visit 1 and final visit, and questions (iv) to (ix) are answered at the final visit.

It is composed of several items

- (i) Ease of insertion (visit 1). This question has the following categories: 1 = very good, 2 = good, 3 = regular, 4 = bad and 5 = very bad; and only one of them will be selected.
- (ii) Subjects pain at the time of insertion (visit 1). This question has the following categories: 1 = without pain, 2 = with little pain, 3 = with moderate pain, 4 = with intense pain and 5 = with unbearable pain; and only one of them will be selected.

- (iii) Visual Analog Scale of pain (VAS) (visit 1 and final visit): this scale is evaluated in 10 points where 10 represents the worst pain suffered during her lifetime and 1 the absence of pain.

Analysis for the VAS will be described as continuous and measured variables through time using the test of comparison of means through the Analysis of Variance (ANOVA) and must be based on the sum of squares type III. The treatment differences regarding the change from baseline, will be assessed through t tests paired within ANOVA, utilizing the difference in means estimated by least squares. These comparisons will be made amongst all treatment groups.

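### The utero-cervical angle is planned in only 60% of pessary women with no rule for choosing them, although the outcome and its analysis cover all; for cervical length the sections conflict

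*Protocol*

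**What the plan says.** - **Protocol 5.4.2.** The angle between the posterior uterine wall and the cervical canal, "in addition to a measurement of the cervical length", taken before and after insertion, "will be performed on 60% of the study participants assigned to one of the two groups with medicated pessary". The next sentence lets the post-insertion scan fall at either of two visits: it "may be performed at visit one or at visit two at the latest". That sentence carries no 60% limit.
- **Protocol 7.2.2.** Cervical length, cervical position and utero-cervical angle before and after insertion are secondary outcomes. No subset is stated. The position item repeats the choice between the insertion day and Visit 2.
- **Protocol 5.5.** The pessary is placed "Once the cervix length and positioning have been examined by transvaginal ultrasound", with no restriction to a subset.
- **Protocol 5.4.3.** At control visits, pessary women are scanned by the specific pessary technique so that length is measured and recorded, again without a 60% limit.
- **SAP section 5, Table 1.** The row "Transvaginal Ultrasound" is marked at every visit. Visit 2 is footnoted as confirmatory.
- **SAP section 10, anatomical cervical changes.** "The length of the cervix and cervical angle variables, will be described as continuous and measured variables through time", by repeated-measures ANOVA with the baseline value as covariate, comparing the pessary groups. The section mentions neither the 60% nor what happens to women who were not measured.

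**The concern.** The protocol's rationale attributes the pessary's effect to moving the cervix backwards and changing its angle, so the angle is the most direct check of the proposed mechanism. Under 5.4.2 a site may leave 40% of pessary women without it, and no rule says which 40%. The SAP gives the analyst no sign of this. A woman without a baseline angle cannot enter a model with baseline as covariate, so the analysis set would be decided by who happened to be measured.

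Two things are at stake. The first is precision, for both the mean change and the comparison of the two doses. The second is interpretation. In an open-label trial, a subset formed without a rule may differ from the full arm, and may differ between sites or doses. The flexible scan time adds to this. A same-day scan shows mainly mechanical displacement. One at the next visit, which may be up to 4 weeks later (5.4.3), also reflects progesterone exposure, which the rationale says may slow cervical maturation.

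**Working it through.** The documents give no sample size, standard deviation (SD) or precision target for the anatomical outcomes, so there is no stated figure to reproduce. The check is of relative precision.

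**Inputs.** Measured share 0.60 (Protocol 5.4.2). Evaluable women: 90 per group, so 2 × 90 = 180 with a pessary (Protocol 9.1). Enrolled pessary women: 198 (Protocol 9.1). Two-sided 95% intervals (SAP section 5).

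**Counts, if the 60% applies to all pessary women.**
- Evaluable: 0.60 × 180 = 108, and 0.60 × 90 = 54 per dose.
- Enrolled: 0.60 × 198 = 118.8, about 119.

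**Standard error.** At equal SD the ratio is √(n / 0.60n) = 1/√0.60 = 1.291, so 29% larger. Seen the other way, full measurement narrows it by 1 − √0.60 = 22.5%.

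**In units of the SD of the change.** The half-width is t(0.975; n − 1)/√n for the mean change with doses pooled, and t(0.975; 2m − 2) × √(2/m) for the difference between doses with m women per dose. The detectable difference uses (1.96 + 0.84) × √(2/m).

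| Quantity | All measured | 60% measured | Ratio |
|---|---|---|---|
| 95% half-width, mean change, doses pooled (180 vs 108) | 0.147 SD | 0.191 SD | 1.297 |
| 95% half-width, difference between doses (90 vs 54 per dose) | 0.294 SD | 0.382 SD | 1.297 |
| Difference between doses detectable at 80% power | 0.42 SD | 0.54 SD | 1.291 |

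**Which women the 60% refers to.** The sentence stands in 5.4.2, which deals with women selected for a short cervix; women enrolled on obstetric history are in 5.4.1. If only a share s of pessary women (not given, between 0 and 1) is eligible for the measurement, the count is 108 × s, so 108 is the upper end.

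**Possible bias.** If measured and unmeasured women differ by d in mean change, the subset mean is off by (1 − 0.60) × d = 0.4d for the whole arm. The documents give no d. As a pure assumption, d between −5 and +5 degrees gives −2 to +2 degrees, and d = 0 gives none.

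**Cervical length.** Read alone, 5.4.2 puts paired length in the same 60%. Set beside it, 5.5 has length examined before placement, 5.4.3 has it recorded at control visits, and SAP Table 1 schedules the scan at every visit, all without a subset. If those sections are followed, length before and after insertion exists for up to all 180 evaluable women and the loss is 0%.

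**The case against.** The best defence is that this is a secondary outcome in an exploratory Phase II trial, with each woman as her own control and no precision target. Measuring a mechanistic variable in a subset is legitimate, 54 women per dose is not trivial, and 29% is not a shortfall against any planned figure. The primary outcome is untouched. Table 1 names the scan only; it does not say that the view needed for the angle is acquired, so there may be a capacity reason for 60%. All of this stands, and it limits the weight of the point.

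Three stronger readings are tempting, and the documents do not support them.

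- *That paired cervical length exists for only 60%.* Protocol 5.4.3 and 5.5 and SAP Table 1 plan length for all pessary women. One caveat is that 5.4.3 contains a clause leaving the scan to the physician's judgement. It reads as attached to the capsule group, but the wording is ambiguous.
- *That the 60% is a convenience sample picked by the unblinded operator.* The documents are silent on who chooses. Selection by dose is not shown either: the participant's sticker distinguishes only pessary from capsule (5.4.3), containers carry codes, and the sponsor keeps the randomisation plan until the database is clean (5.3).
- *That the unmeasured 40% will be women with poor images, early removal or early delivery.* Nothing says so. A same-day scan is allowed, 4 weeks is a maximum interval, and images or visits could be lost for the same reasons under full measurement.

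What the defence does not answer is that the outcome definition and the SAP cover all pessary women, the protocol measures the angle in 60% of them, and no rule connects the two.

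**Conclusion.** The point holds for the utero-cervical angle. The protocol limits it to 60% of pessary women without a selection rule or a single post-insertion time, while the outcome list and the SAP treat it as an outcome of both pessary groups. The cost in precision is a standard error about 29% larger (108 instead of 180 evaluable women, 54 instead of 90 per dose). This assumes equal SD, 90 evaluable women per group, and that the 60% applies to all pessary women, including those enrolled on history. Cervical position is affected in the same way only if it is read from the angle measurement.

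Selection bias is a possibility left open by the missing rule, not a finding; its size cannot be derived from the documents. For cervical length the defect is an inconsistency between sections, with no demonstrated loss of data. The change is worth making because it is cheap and because a subset formed without a rule cannot be repaired afterwards. It does not bear on the primary result.

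**What to change.** 1. **Protocol 5.4.2:** measure the angle in all women in both pessary groups at the scans already scheduled, with one fixed post-insertion time for everyone. Align the timing wording in 7.2.2.
2. **If capacity requires 60%:** have the independent statistician mark a random subset, balanced between the 6.3 g and 7.7 g groups, on the randomisation list before insertion. Name that subset in SAP section 10 as the analysis set for the angle.
3. **Length:** state that it is measured before and after insertion in all pessary women, so that 5.4.2, 5.4.3, 5.5 and SAP Table 1 agree.
4. **Scope:** state whether the angle measurement includes women enrolled on obstetric history (5.4.1).
5. **SAP section 10:** say how women without a baseline or post-insertion angle are handled, and report their number by dose.

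The cost is some extra measurement time on scans already planned (the documents do not say how much), or one extra column on the randomisation list. Full measurement will not prevent losses from poor images or early removal, which is why item 5 is needed in either case.

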## 4 STUDY DESIGN

The study will be conducted in compliance with the protocol, the good clinical practice standards, and the provisions of the corresponding ethics committee.

This will be a randomized, open-label, controlled, multicenter, exploratory Phase II study of efficacy. Pregnant patients with a single fetus who after reading the informed consent voluntarily agree to participate in the study will be included.

For secondary outcomes, patients will be their own controls on the following endpoints to be tested: cervix anatomical features—position and length—; plasma and endometrial progesterone concentrations in non-pregnant menopausal women; surveys on pregnant women to establish the acceptability and tolerance of the intervention; and local and systemic safety issues.

4.1. Pregnant Volunteers: 270 + 10% pregnant women at risk of preterm birth from the 4 participating sites will be recruited. This population will be divided into 3 treatment groups with 90 participants each.

They will be informed and invited to participate in the study at prenatal and/or ultrasound control between 16 and 24 weeks of gestation. Volunteers will be included in all cases up to 24 (0/0) weeks of gestation. Volunteers will be selected on the basis of their clinical history and by transvaginal ultrasound performed between weeks 16 and 24. All volunteers with a single pregnancy and cervical length  $\leq 25$  mm but  $\geq 10$  mm will be invited to participate in the study. Prior to inclusion in the study, fetal vitality or other exclusion factors discussed in detail below will be confirmed. Those patients who do not agree to participate in the study will receive the current standard care at each participating site depending on their condition.

4.1.1. Inclusion criteria in pregnant volunteers:

- Pregnant women with a single fetus with a cervical length of 10-25 mm between 16 and 24 weeks of gestation with no pre-existing risk factors.
- Women with ongoing pregnancy between 16 and 24 weeks of gestation with a single fetus and cervical length  $\geq 10$  mm, and having pre-existing risk factors in the immediately previous pregnancy characterized by:
  - Preterm birth before week 35 (with a viable fetus).
  - Premature rupture of membranes before week 35 (with a viable fetus).

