#### 5.7. Study participant withdrawal

The progesterone cerclage pessary will be removed if the patient requests so, or if there is any adverse event not responding to treatment alternatives such as pathological vaginal discharge non-responsive to antibiotic therapy. These participants will not be replaced and the information collected from them will be included in the analysis since this is based on the intention-to-treat principle.

Follow-up of subjects withdrawn from the investigational product will be the same as the standard follow-up.

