6. POPULATION DEFINITIONS

In order to meet the needs of the sub-groups of the Protocol, the following population sub-groups are defined:

Per Protocol (PP): It is defined as the subset of participants who meet the criteria of selection, who expressed their desire to participate in the study, who signed the informed consent form, that the drug has been administered to them and have completed all the visits required or till the termination of the pregnancy as per Protocol.

Intention to treat (ITT): It is defined as the subset of participants who meet the selection criteria, showing their desire to participate in the study, who signed the informed consent form, that the drug has been administered to them, who have at least completed the initial visit and at least one of the subsequent visits to the pessary referred to in the Protocol.

The main efficacy analysis will be carried out with a focus Per Protocol (PP), however it will also be carried out per Intention to Treat (ITT) all the analysis. Otherwise, the main safety analysis will be completed as ITT.

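### At threatened preterm labour, Protocol 5.4.4 lets a physician who knows the arm decide study continuation, and nothing secures the woman's place in the Per Protocol main efficacy analysis

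*Protocol*

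**What the plan says.** Protocol 5.4.4 covers women who consult for threatened or actual preterm labour. At that moment "the treating physician will be provided with information about the progesterone treatment the patient is receiving in the study". Then "the decision for her continuation in the clinical study will be made jointly as far as possible", and the qualifier is "since the opinion of the treating physician shall predominate". No criteria for the decision are given, and its object is participation in the study, not use of the product.

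The arm is known in any case. Protocol 4 states "This will be a randomized, open-label, controlled, multicenter, exploratory Phase II study of efficacy", and the pregnancy card carries a "self-adhesive sticker detailing their participation in one of the treatment groups (pessary or capsule").

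Protocol 5.4.3 has staff record at each visit "the existence of potential causes for" *ex-post* exclusion from the study. The term is not defined.

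Three other exits carry a statement that the woman is kept in the analysis:
- an expelled pessary not repositioned in time (5.5);
- poor or interrupted capsule use (5.6);
- pessary removal on request or for an unresponsive adverse event (5.7), where "These participants will not be replaced and the information collected from them will be included in the analysis" on the intention-to-treat principle.

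Section 5.4.4 has no such sentence.

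On the analysis side, SAP 6 says "The main efficacy analysis will be carried out with a focus Per Protocol (PP"), with all analyses repeated on its ITT set. The Per Protocol set needs every required visit, or follow-up until the pregnancy ends in line with the protocol. The ITT set needs treatment, the first visit and at least one later visit, so it is not all randomised women.

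**The concern.** Preterm labour is the step immediately before the primary event, spontaneous delivery before 32 and 34 weeks (Protocol 9). An exit at that step depends on the outcome. It may also depend on the arm, because the person whose opinion prevails knows the arm and has no stated criteria to follow.

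If such exits are commoner in one arm and the women are then left out of the analysis set, that arm loses events and looks better with no treatment effect. This route is open in all three arms and needs no pessary removal. It is therefore separate from the rule in SAP 9 that ends participation when a pessary is removed in groups B and C, and correcting SAP 9 would not close it.

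**Working it through.** **Does the text allow the loss?**

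1. *Is the birth still recorded?* Probably. Protocol 5.4.5 closes every case at 36 6/7 weeks or at preterm birth. Protocol 5.8 takes pregnancy outcome from hospital records or the treating physician, and has the records of women in preterm labour before 32 and 34 weeks reviewed to classify the delivery. Protocol 8 requires each preterm birth to be reported within 24 hours.
2. *Is the birth counted in the main analysis?* Not settled. A woman taken out under 5.4.4 may miss later visits. Whether she was followed to the end of pregnancy in line with the protocol depends on how that phrase in SAP 6 is read. SAP 7 has women who did not conclude the study identified before the populations are defined, and its list of reasons includes medical contraindication and an open category.
3. *Is she counted in the Kaplan-Meier analysis?* Protocol 9 and SAP 10 name only elective deliveries as censored. Withdrawal is not addressed.

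**How large could the effect be?**

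Inputs from Protocol 9.1: 90 women per group with data, two-sided alpha 0.05, uncorrected chi-square. The stated 80% power cannot be reproduced because no control rate is given. Nothing below depends on it.

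Assumptions, not in the documents: true event rate r = 20% in every arm; a fraction f of would-be events is lost from one pessary arm and none from the capsule arm; k women who would not have had the event leave with each one who would. The k term is needed because 5.4.4 also covers threatened labour that settles.

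Expected events = 90 × 0.20 = 18.

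Observed pessary rate = 90r(1 − f) / [90 − 90rf(1 + k)]. With k = 0 this is r(1 − f)/(1 − rf).

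The last column is the chance of a significant result favouring the pessary, by exact binomial enumeration with the reduced arm size taken to a whole number.

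| f | k | Observed pessary rate | Ratio to 20% | False benefit |
|---|---|---|---|---|
| 0 | – | 18/90 = 20.0% | 1.00 | 2.4% |
| 25% | 0 | 13.5/85.5 = 15.8% | 0.79 | 10.8% |
| 25% | 1 | 13.5/81 = 16.7% | 0.83 | 7.7% |
| 25% | 2 | 13.5/76.5 = 17.6% | 0.88 | 5.6% |
| 50% | 0 | 9/81 = 11.1% | 0.56 | 35% |
| 50% | 1 | 9/72 = 12.5% | 0.63 | 25% |
| 50% | 2 | 9/63 = 14.3% | 0.71 | 14% |

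Other patterns at r = 20% with k = 0:
- Loss of 25% in the pessary arm and 12.5% in the capsule arm: 15.8% v 15.75/87.75 = 17.9%, ratio 0.88, false benefit 5.5%.
- Loss of 25% in both arms: 2.4%, no inflation.
- Loss in the capsule arm only: the same bias against the pessary.

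Over true rates of 10% to 30% with k = 0, false benefit is 8–13% (a quarter lost) and 21–46% (half lost). Dilution by non-events matters more as r rises. Loss is neutral when k = (1 − r)/r, which is 4 at r = 20% but 2.3 at r = 30%. At r = 30%, f = 25%, k = 2 the observed rate is 20.25/69.75 = 29.0%, ratio 0.97, so almost no bias is left.

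For scale, f = 50% with k = 0 and f = 25% with k = 1 each take 9 of 90 women. That equals the 10% non-completion the plan allows for all causes together. The f = 50%, k = 2 row takes 27.

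**The case against.** The best reply is that in this protocol withdrawal from the study does not mean loss from the analysis. Sections 5.5 and 5.6 withdraw women and still analyse them, 5.7 gives intention to treat as the general basis, and 5.4.5 closes every case with no exception for 5.4.4. SAP 1 also makes the protocol the final reference. On that reading 5.4.4 lacks only a cross-reference. A woman observed to her preterm birth can also still meet the Per Protocol definition, and the ITT set will usually hold her.

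Much of this stands. A reader might infer from 5.4.4 that the births of these women go unrecorded. Protocol 5.4.5, 5.8 and the 24-hour report do not support that. A reader might also take *ex-post* exclusion in 5.4.3 as authority to drop women from the analysis. The text only has potential causes recorded and gives no rule for using them. That the physician is told the arm adds little in an open-label trial.

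What the reply does not settle is the main analysis. SAP 6 puts a completers-type set first, against the protocol's own principle, and neither document says that a woman taken out under 5.4.4 belongs in that set. The SAP's ITT set is a second analysis and is itself not all randomised women.

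**Conclusion.** The point holds in limited form. The outcome is largely collected. The gap is that 5.4.4 does not secure the woman's place in the analysis, and the choice of Per Protocol in SAP 6 lets that gap reach the main efficacy result.

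The documents do not show that exits would be uneven, or which arm they would favour, so it would be wrong to conclude that the trial will be biased towards the pessary. The ranges of 6–11% and 14–35%, against 2.4% with no loss, rest on an assumed 20% rate and on loss from one pessary arm only. The upper ends assume that only women heading for the event leave, the lower ends that two others leave with each of them. Balanced loss causes no inflation. The change is worth making because the exit sits next to the primary event and the repair is cheap.

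**What to change.** - **Protocol 5.4.4:** state that the decision concerns continuing the study product only. Whatever is decided, the date and type of birth are taken from the hospital record (5.8) and counted in the woman's randomised arm.
- **SAP 6:** state that a woman whose product is stopped under 5.4.4 is not excluded from the main efficacy analysis for that reason. Report an analysis of all randomised women alongside Per Protocol, and tabulate 5.4.4 decisions by arm.
- **SAP 10:** state how withdrawal is handled in the Kaplan-Meier analysis.
- **Protocol 5.4.3:** reconcile *ex-post* exclusion with the intention-to-treat statements in 5.5 to 5.7. The authors need to say what the phrase means.

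Decisions on the woman's care stay as they are. The cost is a few lines of text and one extra table. Outcomes already come from hospital records, so no visits are added.
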